6.2 DETAILS OF STUDY PROCEDURES AT SELECTED VISITS

6.2.1 Screening and run-in period(s)

Screening Period

Patients will be eligible to screen and enroll on the same day or day of the baseline visit.

- During the screening visit, demographics information will be collected. This includes:
 - Age (on the day of informed consent, in years)
 - Sex (male, female in order to describe the subject's sex at birth)
 - Gender identity (male, female, non-binary, not answered, or other in order to describe how the trial participant self-identifies, regardless of their genotypic or phenotypic sex) if 1) locally accepted (ie., based on HA/EC/IRB acceptance, independent of acceptance by investigators or participants), 2) investigators are willing to ask, and 3) participants are willing to reply.
 - For women: of childbearing potential yes / no in order to characterize the patient population
 - Ethnicity and race in order to sufficiently characterize the patient population, to support possible subgroup analyses if needed
- Baseline conditions and medical history
- Concomitant medications
- Smoking status
- Pregnancy status (where available)
- Non IPF PF or IPF
- Presence or absence of PPF
- HRCT pattern (historical, within prior 12 months)
- FVC & DLCO (historical, within prior 12 months)

Baseline Conditions & Medical History
Proprietary confidential information © 2022 Boehringer Ingelheim International GmbH or one or more of its affiliated companies

• Will be collected at the Screening/Baseline visit

6.2.2 Intervention period

Patients will receive the cough monitor and conduct cough recordings over a period of 12 weeks from study entry until the End of Study visit.

6.2.3 Study completion

Patients will complete study procedures at Visit 7/EOS and return the cough monitor, provisioned mobile phone and home spirometer at this visit. Completion of study procedures and return of the provisioned equipment at this visit will constitute study completion.

Page 38 of 71

Proprietary confidential information © 2022 Boehringer Ingelheim International GmbH or one or more of its affiliated companies

7. STATISTICAL METHODS AND DETERMINATION OF SAMPLE SIZE

7.1 NULL AND ALTERNATIVE HYPOTHESES

This is an exploratory study with no treatment intervention aiming to assess the use of a new generation of cough monitoring device and describe cough frequency over 12 weeks. No confirmatory testing is performed and hence no null and alternative hypotheses are defined. A justification of the sample size is provided in Section 7.4.

7.2 PLANNED ANALYSES

7.2.1 General considerations

Cough count/hr will be log transformed for analysis. Standard statistical parameters (number of non-missing values, mean, standard deviation (SD), median, quartiles, minimum and maximum) or frequency tables will be calculated where appropriate. All individual data will be listed.

Patient analysis sets:

Entered Set (ES): those patients who were entered into the study.

Additional patient analysis sets may be defined in the SAP.

7.2.2 Handling of Intercurrent Events

This section is not applicable as there is no comparison of interventions.

7.2.3 Primary objective analyses

The cough count (CC) frequency, measured over 4 24-hour recordings in 12 weeks will be analysed as CC/hour and will be log-transformed for data summaries. On each day for which cough monitoring is completed, the log-transformed cough count is calculated as:

Log-transformed cough count = $\log \frac{\text{Number of coughs}}{\text{Length of recorded time (hours)}}$

Cough count for each visit will be reported descriptively. Summary statistics will be tabulated on original scale of CC/hr as well as the geometric mean and 95% confidence intervals after back-transforming the summarized log transformed data. Summary measurements and individual values of CC/hr over time will also be presented graphically.

Additional details will be included in the SAP.

Page 39 of 71

16 Sep 2022

Proprietary confidential information © 2022 Boehringer Ingelheim International GmbH or one or more of its affiliated companies

Protocol

The primary endpoints will be summarized in the same fashion as described above by each subgroup level.

7.2.3.3 Supplementary Analyses

Not applicable

Proprietary confidential information © 2022 Boehringer Ingelheim International GmbH or one or more of its affiliated companies

7.2.4 Secondary objective analyses

Secondary endpoints will be summarized descriptively by visit.

Change from baseline in CC/hr at Week 4, Week 8, and Week 12 will be summarized in terms of absolute changes in CC/hr and in terms of geometric mean ratios. Model based estimates for changes from baseline at Week 12, for example least squares means adjusted for baseline CC/hr or other covariates, may be calculated.

Standard descriptive statistical parameters will be tabulated for all other secondary endpoints.

To assess the relationship between objective cough frequency and FVC (mL), correlations (spearman and Pearson) will be calculated between the following variables:

- Baseline CC/hr (log-transformed) and Baseline FVC (mL)
- Baseline CC/hr (log-transformed) and FVC (mL) at Week 12
- Baseline CC/hr (log-transformed) and change from baseline FVC (mL) at Week 12
- CC/hr at Week 12 (log-transformed) and FVC (mL) at Week 12
- Change in CC/hr at Week 12 (calculated from log-transformed values) and change from baseline in FVC (mL) at Week 12

Graphical presentations of the secondary endpoints and correlations may also be produced. Further details will be included in the SAP.

Page 41 of 71

Proprietary confidential information © 2022 Boehringer Ingelheim International GmbH or one or more of its affiliated companies

7.2.6 Safety analyses

Adverse events will be coded using the Medical Dictionary for Drug Regulatory Activities (MedDRA). Standard BI summary tables and listings will be produced. All enrolled patients will be included in the safety analysis. In general, safety analyses will be descriptive in nature and will be based on BI standards. No hypothesis testing is planned.

Frequency and severity of adverse events related to the study procedure will be tabulated by system organ class and preferred term after coding according to the current version of the Medical Dictionary for Drug Regulatory Activities (MedDRA) at database lock.

Page 42 of 71

Proprietary confidential information © 2022 Boehringer Ingelheim International GmbH or one or more of its affiliated companies

7.2.8 Interim Analyses

Interim analyses will be performed as needed to inform subsequent studies.

7.3 HANDLING OF MISSING DATA

Imputation of missing data will not be done. Unless otherwise noted, analysis will be conducted using all patients with the endpoint available.

Missing or incomplete AE dates will be imputed according to BI standards.

7.4 RANDOMIZATION

but to gain experience using the device in a real-world setting, therefore no randomization is needed for this single group study.

7.5 DETERMINATION OF SAMPLE SIZE

[P22-04417] was a phase 2a study which investigated the effect of inhaled RVT-1601 (cromolyn sodium) on 24-hour average cough counts in patients with IPF. 97 patients were randomized to four arms (RVT-1601 10mg, 40mg, 80mg, or placebo for 12 weeks). The baseline measurements of the mean 24-hour cough count were 38.0 ± 26.6 (RVT-1601 10mg; n=27); 36.8 ± 21.7 (RVT-1601 40mg arm; n=22); 35.7 ± 17.8 (RVT-1601 80mg arm; n=23); 34.3 ± 19.6 (Placebo; n=25).

Assuming we observe similar standard deviations for cough count as the SCENIC trial, the table below reports the 95% confidence interval range we expect for the 24-hour cough count assuming a sample size of 50 patients that are normally distributed. For example, when the sample size is 50, a two-sided 95% confidence interval for a mean will extend 7.484 from the observed mean, assuming that the standard deviation is known to be 27 and the confidence interval is based on the large sample z-statistic.

Table 7.5: 1 Confidence Interval ranges based on N=50 patients for different standard deviations

Standard Deviation	19	21	23	25	27
95% CI Range*	±5.266	±5.821	± 6.375	±6.930	±7.484

*CI Range calculated using the NQuery 8, Version 8.2.7.0 program for "Confidence Interval for One Mean using Normal Distribution"

Proprietary confidential information © 2022 Boehringer Ingelheim International GmbH or one or more of its affiliated companies

8. INFORMED CONSENT, STUDY RECORDS, DATA PROTECTION, PUBLICATION POLICY, AND ADMINISTRATIVE STRUCTURE

The study will be carried out in accordance with the Medical Devices Directive (93/42/EEC) and the harmonised standards for Medical Devices (ISO 14155, current version).

The study will be carried out in compliance with the protocol, the ethical principles laid down in the Declaration of Helsinki, in accordance with the ICH Harmonized Guideline for Good Clinical Practice (GCP), relevant BI Standard Operating Procedures (SOPs), the EU directive 2001/20/EC / EU regulation 536/2014. Investigators and site staff must adhere to these principles. Deviation from the protocol, the principles of ICH GCP or applicable regulations as will be treated as "protocol deviation".

Standard medical care (prophylactic, diagnostic and therapeutic procedures) remains the responsibility of the treating physician of the patient.

The investigator will inform the contracting entity or delegate immediately of any urgent safety measures taken to protect the study patients against any immediate hazard, as well as of any serious breaches of the protocol or of ICH GCP.

The Boehringer Ingelheim transparency and publication policy can be found on the following web page: trials.boehringer-ingelheim.com. The rights of the investigator and of the contracting entity with regard to publication of the results of this study are described in the investigator contract. As a rule, no study results should be published prior to finalisation of the Study Report.

The certificate of insurance cover is made available to the investigator and the patients and is stored in the ISF.

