3. DESCRIPTION OF DESIGN AND STUDY POPULATION

3.1 OVERALL STUDY DESIGN

The proposed pilot is a multi-center, exploratory low-intervention study (without an investigational medicinal product), in which a digitally enabled cough monitoring device will be worn by approximately 50 evaluable subjects with Non IPF pulmonary fibrosis or IPF across sites in North America and Europe.

The eligible subjects will be identified by the participating specialist physicians including pneumologists involved in the diagnosis, treatment, and management of Fibrosing ILD and IPF. The participant selection process will be consecutive, and the participating specialist physicians will be provided guidance to minimize any potential selection bias. Eligible subjects must be previously diagnosed with Non IPF Pulmonary Fibrosis or IPF and will be asked to provide informed consent prior to inclusion in the study.

Consenting subjects will be followed for a maximum period of 12 weeks (Figure 3.1: 1); all subjects will participate in 7 visits, 3 in person and 4 remote visits.

Figure 3.1: 1 Study design

, CC- cough count

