6. INVESTIGATIONAL PLAN

6.1 VISIT SCHEDULE

A multi-center, real-world low intervention pilot study based on newly collected data from approximately 50 evaluable subjects with Non IPF Pulmonary Fibrosis and IPF will be conducted in various sites in the North America and Europe.

The eligible subjects will be identified by the participating specialist physicians including pneumologists involved in the diagnosis, treatment, and management of Non IPF Pulmonary Fibrosis or IPF. The participant selection process will be consecutive, and the participating specialist physicians will be provided guidance to minimize any potential selection bias. Eligible subjects must be previously diagnosed with Non IPF pulmonary fibrosis or IPF and will be asked to provide written informed consent prior to inclusion in the study.

Consenting subjects will be followed for a maximum period of 12 weeks (Figure 3.1: 1); all subjects will participate in 7 clinical visits, 3 in person and 4 remote visits.

During the screening visit (V1) and the baseline visit (V2), baseline data will be collected, including on-site spirometry, historical HRCT pattern (most recent study within the previous 12 months), historical FVC% (most recent value within 6 months prior to V2 & most distant value within 12 mos. of V2), DLCO% predicted (most recent value within 6 months prior to V2 & most distant value within 12 mos of V2),

Where allowed by local regulations, a subject screening log will be kept at each site, recording basic information such as age at Non IPF Pulmonary Fibrosis or IPF diagnosis, sex, information on the eligibility (or reasons for non-eligibility/non-enrollment, including a reason for refusal [if known]) and the study (i.e. having provided informed consent) will be maintained in the Investigator Site File (ISF).

Subjects will be followed prospectively from the time of enrollment until the earliest of death, loss to follow-up or end of the study period. Subjects who are alive and not lost to follow-up, will complete their study participation once study procedures have been completed for Visit 7.

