4. CHANGES IN THE PLANNED ANALYSIS OF THE STUDY

For the endpoint "Cough frequency and number of cough bouts at each of the activity levels (exertion): stationary/low, medium/high", activity levels will be categorized as:

- Low activity
- Medium activity
- High activity

"Stationary" activity represents non-wear time.

Only inspiratory crackles will be summarized for the endpoint "Lung sound events (potentially including, but not limited to, inspiratory crackles)

5. **ENDPOINTS(S)**

5.1 **PRIMARY ENDPOINT(S)**

The primary endpoints as stated in the CTP are: Cough count per hour (CC/hr) measured over a 24-hour period at baseline visit, Week 4(V4), Week 8(V5), Week 12 (V6).

Note that these endpoints are the average CC/hour at each of the 4 visits.

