7.4 PRIMARY ENDPOINT(S)

7.4.1 **Primary analysis of the primary endpoint(s)**

CTP Section 7.2.3: The cough count (CC) frequency, measured over 4 24-hour recordings in 12 weeks will be analysed as CC/hour and will be log-transformed for data summaries. On each day for which cough monitoring is completed, the log-transformed cough count is calculated as:

Log-transformed cough count = $log \frac{Number of coughs}{Length of readable recorded time (hours)}$

Cough count for each visit will be reported descriptively. Summary statistics will be tabulated on original scale of CC/hr as well as the geometric mean and 95% confidence intervals after back-transforming the summarized log transformed data.

Summary measurements and individual values of CC/hr over time will also be presented graphically.

Descriptive statistics, including the coefficient of variation (CV), for cough count/hour will be tabulated by visit using the original scale and for the log (natural) transformed values. In cases where 0 coughs are observed during a recording interval (e.g. night time, low activity duration, or over the 24 hour recording period), 0.1/hr will replace 0 in order to allow for the log transformation. Geometric means, coefficients of variation and 95% CIs be presented as well. For these, the summary measures using the log-transformed values will be calculated then back-transformed to the original scale.

Boehringer Ingelheim TSAP for BI Trial No: 1490-0005

Proprietary confidential information © 2024 Boehringer Ingelheim International GmbH or one or more of its affiliated companies

Plots of the geometric means and geometric mean ratios over time will be produced. Individual time profiles for CC/hr will also be presented graphically.

The primary endpoints will be summarized in the same fashion as described above by each subgroup level listed in Section 6.4.

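### Does N=50 need a precision statement for the geometric mean, when Protocol 7.5 gives one only for an arithmetic mean?

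*Protocol*

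**What the plan says.** Protocol 7.5 takes baseline cough counts from the four arms of an earlier trial in IPF and tabulates the half-width of a 95% interval for one mean at N=50, for standard deviations of 19 to 27. Its worked example reads "when the sample size is 50, a two-sided 95% confidence interval for a mean will extend 7.484 from the observed mean". It states its assumptions: normal data, known SD, large-sample z.

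For the primary endpoint, Protocol 7.2.3 plans summaries on the original scale "as well as the geometric mean and 95% confidence intervals after back-transforming the summarized log transformed data". SAP 7.4.1 agrees: for the geometric means, coefficients of variation and intervals, "the summary measures using the log-transformed values will be calculated then back-transformed to the original scale". The general statistics in Protocol 7.2.1 are "number of non-missing values, mean, standard deviation (SD), median, quartiles, minimum and maximum"; SAP section 7 has a similar list. Neither list contains a confidence interval.

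Two smaller points touch the same number:

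- **Enrolled or evaluable.** Protocol 3.1 says the device "will be worn by approximately 50 evaluable subjects", and 6.1 has "approximately 50 evaluable subjects with Non IPF Pulmonary Fibrosis and IPF". The synopsis gives a total of 50, and 3.3 targets enrolment of 25 plus 25. Under Protocol 7.3, "Imputation of missing data will not be done".
- **Unit.** Protocol 7.5 speaks of a 24-hour cough count, while SAP 5.1 says of the primary endpoints: "Note that these endpoints are the average CC/hour at each of the 4 visits".

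**The concern.** The only visible justification of N describes an interval that the plan does not name, and the interval that it does name has no stated precision. The two differ in kind. The tabulated one is additive and symmetric around an arithmetic mean. The planned one is multiplicative and asymmetric around a geometric mean, and its width depends on a log-scale SD that the documents do not give. Describing cough frequency is the primary objective, and the geometric mean is a summary that a later cough study would probably use. If the table gave a flattering picture of that interval, the study might be less informative than it appears. If 50 is the number enrolled, it is also a ceiling on the number contributing at any visit.

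**Working it through.** **1. The plan's own figures.** Half-width = 1.960 × SD / √50. For SD 27: 1.960 × 27 / 7.071 = 7.484. SDs of 19, 21, 23 and 25 give 5.266, 5.821, 6.375 and 6.930. All five entries of Table 7.5: 1 reproduce.

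**2. Inputs for the geometric mean.** The arms in Protocol 7.5 are 38.0 ± 26.6 (n=27), 36.8 ± 21.7 (n=22), 35.7 ± 17.8 (n=23) and 34.3 ± 19.6 (n=25).

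Weighted mean = (38.0×27 + 36.8×22 + 35.7×23 + 34.3×25) / 97 = 3514.2 / 97 = 36.23.

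No log-scale SD is given, so I assume a log-normal distribution, with CV = SD / mean:

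- log SD = √ln(1 + CV²)
- geometric mean = mean / √(1 + CV²)
- 95% limits = geometric mean ÷ and × exp(q × log SD / √n), with q the z or t quantile

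For SD 27: CV = 27 / 36.23 = 0.745, log SD = 0.665, geometric mean = 29.05. The z factor is exp(1.960 × 0.665 / 7.071) = 1.202 and the t factor (49 df) is 1.208. The limits are 24.2 to 34.9 (z) or 24.1 to 35.1 (t).

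**3. The two intervals in relative terms, n=50.**

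| SD | Stated half-width | As % of 36.23 | Log SD | z factor | Geometric mean, relative (z) | t factor |
|---|---|---|---|---|---|---|
| 19 | 5.266 | ±14.5% | 0.493 | 1.146 | −12.7% / +14.6% | 1.150 |
| 21 | 5.821 | ±16.1% | 0.538 | 1.161 | −13.9% / +16.1% | 1.165 |
| 23 | 6.375 | ±17.6% | 0.582 | 1.175 | −14.9% / +17.5% | 1.180 |
| 25 | 6.930 | ±19.1% | 0.624 | 1.189 | −15.9% / +18.9% | 1.194 |
| 27 | 7.484 | ±20.7% | 0.665 | 1.202 | −16.8% / +20.2% | 1.208 |

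On the same z basis, the upper side of the geometric-mean interval nearly equals the tabulated half-width as a percentage, and the lower side is somewhat shorter. Using t makes little difference. These comparisons depend only on the CV, so they hold whatever unit is attached to the source figures.

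**4. Fewer usable recordings.** If 40 rather than 50 recordings are usable (my assumption), the t factor across the table's SDs runs from 1.171 to 1.237, against 1.150 to 1.208 at 50.

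**The case for a change.** The strongest argument for acting is that the table cannot show what drives geometric-mean precision. SAP 7.4.1 replaces a zero count by 0.1 per hour before taking logs, and this includes a zero over the whole 24 hours. Suppose 49 recordings have geometric mean 31 and log SD 0.557 (the value implied by the cited trial's pooled SD of 21.9), and one is set to 0.1. The log distance is ln(31 / 0.1) = 5.74. The variance becomes (48 × 0.557² + 0.98 × 5.74²) / 49 = 0.96, so the log SD is 0.98 and the t factor rises from 1.17 to 1.32. The arithmetic mean would hardly move. This cohort, mixed in diagnosis and enriched for cough, may also vary more on the log scale than the cited trial.

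The arithmetic stands, but the premise is hypothetical: nothing in the documents suggests that a full day without cough is likely, and they support no log SD beyond about 0.47 to 0.67, the range implied by the four source arms and the table's SDs. A wider range would be the reviewer's own choice. The actual spread will be visible in the log-scale SD and the interval reported at each visit.

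Nor is the arithmetic scale foreign to the report. Protocol 7.2.3 and SAP 7.4.1 plan original-scale summaries by visit, and the standard set includes mean and SD, so a reader can compute the interval in 7.5 from tabulated values. On the unit, 7.5 first describes the source measure as a 24-hour average and 7.2.3 divides the count by recorded hours, so a rate per hour is the natural reading. On enrolled or evaluable, 3.1 and 6.1 say approximately, and 7.3 already bases each analysis on patients with the endpoint available, so an N that varies by visit is expected.

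**Conclusion.** The justification and the planned interval do not match, but the plan can stand. The tabulated figures are correct under their stated assumptions and are a fair guide to the planned interval: at n=50 and SDs of 19 to 27, the geometric mean would be known to within a factor of about 1.15 to 1.21 (t-based), against ±14.5% to ±20.7% in the table. This rests on log-normality and on a mean and SDs like those of the cited trial. Protocol 7.1 rules out confirmatory testing and no precision target is set, so no different N follows. A line giving the factor, a unit label and one term for the 50 patients would be tidier, but would alter neither the analysis nor any conclusion.

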8.1 STUDY APPROVAL, PATIENT INFORMATION, INFORMED CONSENT

This study will be initiated only after all required legal documentation has been reviewed and approved by the respective Institutional Review Board (IRB / Independent Ethics Committee (IEC and competent authority (CA) according to national and international regulations. The same applies for the implementation of changes introduced by amendments.

Prior to patient participation in the study, written informed consent must be obtained from each patient (or the patient's legally accepted representative) according to ICH-GCP and to the regulatory and legal requirements of the participating country. Each signature must be personally dated by each signatory and the informed consent and any additional patient-information form retained by the investigator as part of the study records. A signed copy of the informed consent and any additional patient or the patient's legally accepted representative.

The patient must be given sufficient time to consider participation in the study. The investigator or delegate obtains written consent of the patient's own free will with the informed consent form after confirming that the patient understands the contents. The investigator or delegate must sign (or place a seal on) and date the informed consent form. If a study collaborator has given a supplementary explanation, the study collaborator also

Proprietary confidential information © 2022 Boehringer Ingelheim International GmbH or one or more of its affiliated companies

signs (or places a seal on) and dates the informed consent.

Re-consenting may become necessary when new relevant information becomes available and should be conducted according to the contracting entity's instructions.

The consent and re-consenting process should be properly documented in the source documentation.

